- Minimisation of the temporary disruption of arterial flow, which occurs with arterial clamping during surgical closure
- Reduction in scaring compared to surgical cut-down (as VCD use is percutaneous)

Schedule of Events

A schedule of study events is provided in Table 1 below as a guide. This is a tabular summary of the study activities and related scheduled procedures to be performed.

Table 1- Schedule of Study Events for Reference Only

Schedule of Events	Screening	Pre-Proc.	Peri- Proc.	Immed Post Proc.	Post Procedure			
					Approx. 30 mins post	Post 1hr	pre- discharg e	Follow-Up (1 & 3 Months)
Determine Eligibility	√	V	V					
Obtain Informed Consent	√							
Demographic Information	√							
Patient Medical History	√							
Physical Examination	√							
Laboratory Results (within 7 days pre-procedure)	V							
CT Angiogram (May be within 4 months pre-procedure)	√***		,				*	
Angiogram	√***		V	*			*	
Duplex Ultrasound				*	*	*	*	√ * *
Pulses		$\sqrt{}$		$\sqrt{}$	$\sqrt{}$		$\sqrt{}$	$\sqrt{}$
ABI	$\sqrt{}$							√****
Record procedure sheath size & details of graft/valve			$\sqrt{}$					
ACT before PerQseal® closure device insertion			$\sqrt{}$					
Estimate tissue tract depth								
Record PerQseal® details								
Time to deploy PerQseal® closure device			V					
PerQseal® device TTH			V					
Alternative therapy required			√					
PerQseal® device performance assessment				V				
Time from PerQseal® Introducer insertion to PerQseal® closure device deployment				V				
Overall procedural time								
Time to Ambulation					V	V		
Adverse Event Assessment			V		V	√		V

^{*}If Necessary, **3 month follow-up only otherwise if necessary, ***Either a CT Angiogram or Angiogram can be performed, **** at 1 month only if the patient has both dorsalis pedis and posterior tibial pulses absent in the ipsilateral leg.

Viva

DOC-DP2-68 CLINICAL INVESTIGATION PLAN SYNOPSIS FRONTIER IV REV AB

Definitions

Major Vascular Access Site Complication – In the context of this CIP and related to the femoral artery access site, major complications* are any of:

- Major vascular access site complications leading to death, life-threatening (BARC type 5) or major bleeding (BARC type 3a), visceral ischemia or neurological impairment; OR
- Distal embolization from the vascular access site requiring surgery or resulting in amputation or irreversible end-organ damage; OR

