- The use of unplanned endovascular or surgical intervention associated with access site related death, major bleeding (BARC type 3a), visceral ischemia or neurological impairment; OR
- Any access site related new ipsilateral lower extremity ischemia documented by patient symptoms, physical exam, and/or decreased or absent blood flow on lower extremity angiogram; OR
- Surgery for access site-related nerve injury; OR
- Permanent access site-related nerve injury; OR
- Access-site-related infection requiring intravenous antibiotics and/or extended hospitalization
- * Adapted from VARC-21.

Minor Vascular Access Site Complications – In the context of this CIP and related to the femoral artery access site, minor complications* are any of:

- · Access site or access-related vascular injury
 - Dissection
 - > Stenosis
 - Perforation
 - > Rupture
 - Arteriovenous fistula
 - Pseudoaneuysms (> 3 cm)
 - > Haematoma (> 6 cm)
 - Percutaneous closure device failure

not leading to death, life-threatening or major bleeding*, visceral ischaemia or neurological impairment.

- Distal embolization from the vascular access site treated with embolectomy and/or thrombectomy and not resulting in amputation or irreversible endorgan damage.
- Localized access site infection treated with intramuscular or oral antibiotics.
- Any access site related unplanned endovascular stenting or unplanned surgical intervention not meeting the criteria for a major vascular complication.

¹ Kappetein AP, Head SJ, Généreux P, et al. Updated standardized endpoint definitions for transcatheter aortic valve implantation: the Valve Academic Research Consortium-2 consensus document. European Journal of Cardio-Thoracic Surgery 42 (2012) S45–S60.

Viva sure

DOC-DP2-68 CLINICAL INVESTIGATION PLAN SYNOPSIS FRONTIER IV REV AB

- Access site related vascular repair or the need for vascular repair (via surgery, ultrasound-guided compression, transcatheter embolization, or stent graft)
- Failure of a closure device to achieve haemostasis at the arteriotomy site leading to alternative treatment (other than manual compression or adjunctive endovascular ballooning)

BARC Bleeding Definitions Life-threatening or disabling bleeding

- Fatal bleeding (BARC type 5) OR
- Bleeding in a critical organ, such as intracranial, intraspinal, intraocular, or pericardial necessitating pericardiocentesis, or intramuscular with compartment syndrome (BARC type 3b and 3c) OR

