- xx. **Source Data Verification (SDV)** Evaluation of the conformity of the data presented in eCRFs with source data (medical records/notes, lab results, x-rays, etc.).
- xxi. **Ankle-brachial index (ABI)** The ratio of ankle systolic pressure to the arm systolic pressure, used in assessing the status of lower extremity arteries. It is calculated by dividing the higher of the left and right ankle pressures by the higher of the two brachial artery pressures.
- xxii. Time from PerQseal[®] Introducer insertion to PerQseal[®] closure device deployment defined as the time from insertion of the PerQseal[®] Introducer to complete removal of the PerQseal[®] closure device and Introducer-sheath from the patient following deployment.

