8. STUDY DESIGN

This study will be a prospective, multi-centred, non-randomized study to investigate the safety and performance of the PerQseal® in 75 patients in approximately 10 European investigational sites. The study shall not be blinded prior to, during or post the procedure. All patients undergoing an endovascular procedure requiring an arteriotomy created by 12 to 20 F sheaths, via the common femoral artery will be screened against the inclusion/exclusion criteria.

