9.3 Study population

Patients will not be excluded on the basis of age, race, concomitant therapy or co-existing disease. Each centre will continue to enrol eligible patients until a minimum combined Clinical Investigation population of 75 patients is achieved.

Patients with bilateral percutaneous access in the common femoral arteries where both arteries meet all eligibility criteria may, at the discretion of the investigator, both be closed with the PerQseal® closure device. If a PerQseal® is used on the contralateral femoral artery then this will be treated as an independent closure i.e. each limb will be counted as a separate closure only for the purposes of Performance Analysis.

Consented patients who receive contact with the PerQseal[®] closure device become an enrolled subject.

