11.10 Missing data

Historically (which includes 120 subjects and 136 closures across all Frontier studies) there have not been any device related access site complications beyond patient discharge from hospital. So it is expected that all safety data will be captured for all enrolled subjects. All subjects with available data will be used in the statistical analyses. All implanted subjects will be assessed for technical success. With regard to assessment of device related complications through 1 months, data on all subjects through the point of last follow up prior to or at 1 months will be included in the analysis. For the primary analysis, no imputation is expected to be performed for missing data. However, in the unlikely event that there is missing critical safety data Bayesian models may be utilised for sensitivity to investigate the impact of incomplete follow-up.

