	N	Mean	Median	Standard deviation	IQR	Min - Max
If yes, estimate percentage	XX	XX.X	XX.X	XX.X	xx.x – xxx.x	xx.x – xxx.x
Measurement of common femoral artery (mm)	xx	XX.X	XX.X	x.x	xx.x – xx.x	xx.x – xx.x

DOC-DP2-81 Rev 01

Table 13. Device and deployment details

	N	Mean	Median	Standard deviation	IQR	Min - Max
Procedure time (minutes)	XX	XXX.X	XXX.X	XX.X	xxx.x – xxx.x	xxx.x – xxx.x
Angle of device during deployment (°)						
Time taken to deploy the device from introduction into the	XX	XX.X	XX.X	X.X	xx.x - xx.x	xx.x - xx.x
introducer sheath to procedural sheath and device						
removal (minutes)						
Time from the PerQseal® device and introducer sheath	XX	XX.X	XX.X	X.X	XX.X - XX.X	xx.x - xx.x
removal to haemostasis for the access site arteriotomy						
(minutes)						
	% (n/N)					
Device malfunction during use	xx.x (xx/xx)					
Bleeding						
None	xx.x (xx/xx)					
Ooze	xx.x (xx/xx)					
Brisk	xx.x (xx/xx)					
Pulsatile	xx.x (xx/xx)					

DOC-DP2-81 Rev 01

Table 14. Post-procedural angiogram of femoral vasculature

	% (n/N)					
Evidence of leakage from	xx.x (xx/xx)					
arteriotomy						
Evidence of stenosis of artery	xx.x (xx/xx)					
	N	Mean	Median	Standard	IQR	Min - Max
				deviation		
If yes, estimate percentage	XX	XX.X	XX.X	XX.X	xx.x – xxx.x	xx.x – xxx.x

DOC-DP2-81 Rev 01

Table 15. Pre-discharge examination

	N	Mean	Median	Standard deviation	IQR	Min - Max
Time to ambulation (hours post-procedure)	XX	XXX.X	XXX.X	XX.X	xxx.x - xxx.x	xxx.x – xxx.x
Time to actual discharge (hours post-procedure)	xx	XXX.X	XXX.X	XX.X	xxx.x - xxx.x	xxx.x - xxx.x

DOC-DP2-81 Rev 01

Table 16. Groin condition

		Immediate p	ost-	30 min pos	st-	1 hours po	ost-	Pre-disch	arge	1 month		3 month	
		procedure		procedure		procedure	procedure						
		Left leg	Right leg	Left leg	Right leg	Left leg	Right leg	Left leg	Right leg	Left leg	Right leg	Left leg	Right leg
Ipsilateral groin	Normal - % (n/N)	xx.x (xx/xx)	xx.x (xx/xx)	XX.X									
condition	, ,			(xx/xx)									
	Haematoma - %	xx.x (xx/xx)	xx.x (xx/xx)	xx.x (xx/xx)									
	(n/N) Bleeding - % (n/N)	xx.x (xx/xx)	xx.x (xx/xx)	XX.X									
	5 , ,			(xx/xx)									
	Ecchymosis - % (n/N)	xx.x (xx/xx)	xx.x (xx/xx)	xx.x (xx/xx)									
	Other - % (n/N)	xx.x (xx/xx)	xx.x (xx/xx)	xx.x (xx/xx)									

Table 17. ABI

	Baseline		3 Month	
	Left	Right	Left	Right
N	XX	XX	XX	XX
Mean	X.XX	X.XX	X.XX	X.XX
Median	X.XX	X.XX	X.XX	X.XX
Standard	X.XX	X.XX	X.XX	X.XX
deviation				
IQR	X.XX - X.XX	X.XX - X.XX	x.xx - x.xx	X.XX - X.XX

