Min	X.XX	X.XX	X.XX	X.XX
Max	X.XX	X.XX	X.XX	x.xx

Table 18. Lower extremity pulses (palpate)

		Pre-		Imme	diate	30 mi	n	1 hou	r post-	Pre-		1 mor	nth	3 mor	nth
		proce	dure	post-		post-		proce	dure	disch	arge				
				proce	dure	proce	dure								
		Left	Rig	Left	Rig	Left	Rig	Left	Rig	Left	Rig	Left	Rig	Left	Rig
		leg	ht	leg	ht	leg	ht	leg	ht	leg	ht	leg	ht	leg	ht
			leg		leg		leg		leg		leg		leg		leg
Dorsa	Strong	XX.X	XX.X	XX.X	XX.X	XX.X	XX.X	XX.X	XX.X	XX.X	XX.X	XX.X	XX.X	XX.X	XX.X
lis	- %	(xx/	(xx/	(xx/	(xx/	(xx/	(xx/	(xx/	(xx/	(xx/	(xx/	(xx/	(xx/	(xx/	(xx/
pedis	(n/N)	xx)	xx)	xx)	xx)	xx)	xx)	xx)	xx)	xx)	xx)	xx)	xx)	xx)	xx)
	Normal	XX.X	XX.X	XX.X	XX.X	XX.X	XX.X	XX.X	XX.X	XX.X	XX.X	XX.X	XX.X	XX.X	XX.X
	- %	(xx/	(xx/	(xx/	(xx/	(xx/	(xx/	(xx/	(xx/	(xx/	(xx/	(xx/	(xx/	(xx/	(xx/
	(n/N)	xx)	xx)	xx)	xx)	xx)	xx)	xx)	xx)	xx)	xx)	xx)	xx)	xx)	xx)
	Diminis	XX.X	XX.X	XX.X	XX.X	XX.X	XX.X	XX.X	XX.X	XX.X	XX.X	XX.X	XX.X	XX.X	XX.X
	hed - %	(xx/	(xx/	(xx/	(xx/	(xx/	(xx/	(xx/	(xx/	(xx/	(xx/	(xx/	(xx/	(xx/	(xx/
	(n/N)	xx)	xx)	xx)	xx)	xx)	xx)	xx)	xx)	xx)	xx)	xx)	xx)	xx)	xx)
	Absent	XX.X	XX.X	XX.X	XX.X	XX.X	XX.X	XX.X	XX.X	XX.X	XX.X	XX.X	XX.X	XX.X	XX.X
	- %	(xx/	(xx/	(xx/	(xx/	(xx/	(xx/	(xx/	(xx/	(xx/	(xx/	(xx/	(xx/	(xx/	(xx/
	(n/N)	xx)	xx)	xx)	xx)	xx)	xx)	xx)	xx)	xx)	xx)	xx)	xx)	xx)	xx)
Poste	Strong	XX.X	XX.X	XX.X	XX.X	XX.X	XX.X	XX.X	XX.X	XX.X	XX.X	XX.X	XX.X	XX.X	XX.X
rior	- %	(xx/	(xx/	(xx/	(xx/	(xx/	(xx/	(xx/	(xx/	(xx/	(xx/	(xx/	(xx/	(xx/	(xx/
tibial	(n/N)	xx)	xx)	xx)	xx)	xx)	xx)	xx)	xx)	xx)	xx)	xx)	xx)	xx)	xx)
	Normal	XX.X	XX.X	XX.X	XX.X	XX.X	XX.X	XX.X	XX.X	XX.X	XX.X	XX.X	XX.X	XX.X	XX.X
	- %	(xx/	(xx/	(xx/	(xx/	(xx/	(xx/	(xx/	(xx/	(xx/	(xx/	(xx/	(xx/	(xx/	(xx/
	(n/N)	xx)	xx)	xx)	xx)	xx)	xx)	xx)	xx)	xx)	xx)	xx)	xx)	xx)	xx)
	Diminis	XX.X	XX.X	XX.X	XX.X	XX.X	XX.X	XX.X	XX.X	XX.X	XX.X	XX.X	XX.X	XX.X	XX.X
	hed - %	(xx/	(xx/	(xx/	(xx/	(xx/	(xx/	(xx/	(xx/	(xx/	(xx/	(xx/	(xx/	(xx/	(xx/
	(n/N)	xx)	xx)	xx)	xx)	xx)	xx)	xx)	xx)	xx)	xx)	xx)	xx)	xx)	xx)
	Absent	xx.x	XX.X	xx.x	XX.X	xx.x	XX.X	XX.X	xx.x	XX.X	XX.X	xx.x	xx.x	XX.X	XX.X
	- %	(xx/	(xx/	(xx/	(xx/	(xx/	(xx/	(xx/	(xx/	(xx/	(xx/	(xx/	(xx/	(xx/	(xx/
	(n/N)	xx)	xx)	xx)	xx)	xx)	xx)	xx)	xx)	xx)	xx)	xx)	xx)	xx)	xx)

Table 19. 3 Month Duplex ultrasonography

		At a point estimated to be the punctur
		site
	N	xx
	Mean	XX.X
	Median	XX.X
Femoral artery diameter – mediolateral plane (mm)	SD	XX.X
	IQR	xx.x - xxx.x
	Min	xx.x
	Max	xxx.x
	N	xx
	Mean	xx.x
Femoral artery diameter – anteroposterior plane (mm)	Median	xx.x

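### SAP Tables 17 and 18 summarise ABI and pulses by left and right leg, without naming the treated leg or showing change from baseline, so they cannot show a new treated-leg deficit

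*SAP*

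**What the plan says.** SAP 16.1 plans two displays of distal flow. The shell headed "Table 18. Lower extremity pulses (palpate" has a left-leg and a right-leg column at each of seven time points, from before the procedure to 3 months. Its rows are the percentages of strong, normal, diminished and absent pulses. Table 17 gives summary statistics for ABI under left and right, at baseline and at 3 months. Neither shell names the treated leg, says which legs are entered, or has a column for change or shift. SAP 11.3, 11.8 and 11.9 plan no further analysis of pulses or ABI.

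Other parts of the documents are specific about the leg:

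- One component of the major complication (Protocol, Definitions; also SAP 4.2) is "Any access site related new ipsilateral lower extremity ischemia documented by patient symptoms, physical exam" or by reduced flow on angiogram.
- The footnote to the protocol's schedule of events calls for ABI "at 1 month only if the patient has both dorsalis pedis and posterior tibial pulses absent in the ipsilateral leg". Table 17 has no 1-month column for the result.
- Table 16, directly before these two, also uses left and right columns, but its row label begins "Ipsilateral groin".
- Treated leg is a column in List 7, and Table 7 summarises the side of the planned puncture.

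SAP 4.2 defines ABI for the patient and not for the leg: "It is calculated by dividing the higher of the left and right ankle pressures by the higher of the two brachial artery pressures".

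**The concern.** The ischaemia component turns on two ideas: the finding must be new, and it must be in the leg that was closed. The first needs each leg compared with itself before the procedure; the second needs the treated leg identified. Tables 17 and 18 do neither.

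Some legs may well start with weak pulses. The exclusion for peripheral vascular disease is aimed at severe disease, and Table 6 still counts patients with clinically significant disease. A percentage of diminished pulses at 3 months therefore does not say how many are new.

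The study is unblinded and has no concurrent control. Pulses and ABI taken on a schedule are among the few measurements that do not depend on someone deciding to report an event. As drawn, the tables do not let a reader check the reported events against them.

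**Working it through.** The point is about table layout, so the plan has no figure to reproduce. The illustrative inputs are:

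- Patients: 75, from SAP 8 ("in 75 patients in approximately 10 European investigational sites").
- Bilateral share b: SAP 11.10 describes earlier experience ("which includes 120 subjects and 136 closures across all Frontier studies"). If no subject had more than two closures (an assumption), 136 − 120 = 16 were bilateral, so b = 16/120 = 13.3%. The alternative b = 0 is also shown.
- Share f of unilateral accesses on the right: not given; 50% and 80% are assumed.
- New pulse loss: assumed in 10% of treated legs and in no other legs.

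**Step 1, cancellation.** Suppose one leg in a column goes from normal to absent and another from absent to normal. The column has the same number of normal and absent pulses before and after, so Table 18 shows no change. A shift table shows one leg lost. This holds whichever legs are entered.

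**Step 2, dilution, only if both legs are entered.** The treated fraction is f(1 − b) + b in the right column and (1 − f)(1 − b) + b in the left. Multiply by 10 points for the visible rise.

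| f | b | Right column | Left column |
|---|---|---|---|
| 50% | 0 | 0.500 × 10 = 5.0 | 0.500 × 10 = 5.0 |
| 50% | 13.3% | 0.567 × 10 = 5.7 | 0.567 × 10 = 5.7 |
| 80% | 0 | 0.800 × 10 = 8.0 | 0.200 × 10 = 2.0 |
| 80% | 13.3% | 0.827 × 10 = 8.3 | 0.307 × 10 = 3.1 |

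Averaged over both columns the factor is (1 + b)/2, so dilution disappears only if every patient is bilateral. If per-leg ABI is entered for both legs, a mean fall of 0.10 in treated legs would show as 0.05 per column with f = 50% and b = 0.

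**Step 3, if only treated legs are entered.** There is no dilution. At the earlier ratio, 75 × 136/120 = 85 treated legs would be split by side to no purpose, and Step 1 still applies.

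**Step 4, ABI.** Under SAP 4.2, take both ankles and the arm at 130 mmHg, so ABI = 130/130 = 1.00. If the treated ankle falls to 78, the higher ankle is still 130 and ABI stays at 1.00. The value for that leg alone is 78/130 = 0.60. The definition yields one number per patient and cannot fill Table 17's two columns.

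**Step 5, other outputs.** Table 24 has a row for new ipsilateral ischaemia but stops at 1 month. Table 25 runs to 3 months, covers minor complications, and has no ischaemia row beyond a general category for others. SAP 11.8 promises cumulative major-complication rates at all time points, but not by type. Lists 4 to 6 have no leg column. A pulse loss that nobody reports as an event would appear in no planned output as a new loss in a treated leg.

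**The case against.** The strongest reply is that nothing shows the legs are mixed. Table 16 uses the same side columns under an ipsilateral label, so the template can hold treated legs only, and the protocol's schedule lists pulses without saying which leg. This stands. A reader might infer that treated and untreated legs are pooled; the shells leave it open, and the case report form is not in the documents. The dilution figures are therefore conditional. The missing within-leg change does not depend on the answer.

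A second reply is that real ischaemia is not lost. If reported, it is a major complication, appears by type in Table 24 up to 1 month, reaches Table 2 if device related, and goes to adjudication (List 6). The 3-month duplex also examines the puncture site. This stands too. A reader might infer that the primary endpoint would be undercounted; the documents do not support that, since Tables 17 and 18 feed no test.

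Third, it is tempting to treat the other leg as an untouched control. With bilateral access, use of the device on both sides is at the investigator's discretion and requires both arteries to be eligible, so a leg without the device may have been punctured and closed another way.

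Finally, limbs count separately for performance only (SAP 9.3: "each limb will be counted as a separate closure only for the purposes of Performance Analysis"). A descriptive table by treated leg leaves the per-subject safety analysis as it is.

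**Conclusion.** The point holds as a gap in descriptive safety reporting. Followed as written, Tables 17 and 18 cannot show a new deficit in a treated leg, because they give marginal percentages and means with no within-leg comparison and no identification of the treated leg. That part needs no assumption.

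The dilution is a further, conditional loss. It requires both legs to be entered, and its size depends on the assumed side split and bilateral share; the 10-point loss and the 0.10 fall in ABI are illustrations, not expected effects. The ABI part also depends on settling the definition.

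The primary endpoint, its error rate and its power are unchanged. What is lost is a systematic check on event reporting, most clearly between 1 and 3 months. This is an improvement available at almost no cost, not a flaw that threatens the main conclusion.

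**What to change.** - **Pulses.** Tabulate by PerQseal-treated leg, with patients treated on both sides contributing two legs. Add a shift table from pre-procedure to each later visit, with the number of treated legs that drop one or more grades.
- **Other leg.** Where it was recorded, show it separately, distinguishing legs never punctured from legs accessed but closed by another method.
- **ABI.** First reconcile the one-value-per-patient definition in SAP 4.2 with the per-leg columns of Table 17. Then report the paired change from baseline to 3 months in treated legs, provided pressures are held per leg.
- **Labels.** State in each table which legs are included.

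The cost is table programming only. Pre-procedure pulses and the treated side are already planned data, and SAP 16 lets shells be revised without reissuing the SAP if Section 11 is not invalidated, which these changes do not do. If the ABI mismatch is settled by changing the definition, that is a short edit to SAP 4.2.

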16.2 Lists to be generated

List 1. List of all centres that have enrolled subjects (colour coded by country).

Site No.	Name of Hospital	Principle Investigator	Site Address

List 2. Discontinued subjects

Centre ID	Subject ID	Last	Reason for discontinuation
		contact	

List 3. Protocol deviations

Centre ID	Subject ID	Associated evaluation	Deviation type

DOC-DP2-81 Rev 01

List 4. Non-serious adverse events

Centre	Subject ID	Event	Procedure	Start	Days since	Unanticipated	Directly	Resolution	Outcome
ID		type	date	date	procedure	event	associated	date	
							with the		
							device		

List 5. Serious adverse events

Centre	Subject	Event	Procedure	Start	Days since	Reason	Unanticipated	Directly	Resolution	Outcome
ID	ID	type	date	date	procedure	for	event	associated	date	
						serious		with the		
								device		

List 6. CEC adjudications

Centre ID	Subject ID	Event type	Event	Occurred	Serious	Related to	Related to	Severity	Type of
			description	during		the device	the		complication
							procedure		

DOC-DP2-81 Rev 01

[figure not shown]
List 7. Demographics

Centre ID	Subject ID	Type of	Gender	Age	Weight	Height	ВМІ	Largest	Treated leg
		procedure						procedural	
								sheath size	
								used	

16.3 Figures to be generated

Figure 1. Subject disposition

